2.7.2 Secondary Objectives and Endpoints

The secondary study objectives and endpoints to be evaluated in this study are presented in Table 2.

Fable 2 Secondary Study	Objectives	and Endpoints
--------------------------------	-------------------	---------------

Objective	Endpoint	
To investigate the biodistribution of ⁶⁴ Cu-SAR-bisPSMA.	Biodistribution of ⁶⁴ Cu-SAR-bisPSMA on the Day 0 and Day 1 scan:	
	• Maximum and mean SUVs in lesion(s), visceral/soft tissue, bone.	
	Lesion-to-background ratio.	
To assess the participant-level PPV of ⁶⁴ Cu-SAR-bisPSMA PET/CT.	• Participant-level PPV, defined as the proportion of TP participants on the Day 0 scan out of all participants with a positive Day 0 scan.	
	• Participant-level PPV, defined as the proportion of TP participants on the Day 1 scan out of all participants with a positive Day 1 scan.	
To assess the participant-level DR of ⁶⁴ Cu-SAR-bisPSMA PET/CT.	• Participant-level DR, defined as the proportion of participants with a positive Day 0 scan out of all participants with a Day 0 scan.	
	• Participant-level DR, defined as the proportion of participants with a positive Day 1 scan out of all participants with a Day 1 scan.	

To assess the FPR ⁶⁴ Cu-SAR- bisPSMA PET/CT.	• Participant-level FPR, defined as the proportion of FP participants on the Day 0 scan out of all participants with a positive Day 0 scan.
	• Participant-level FPR, defined as the proportion of FP participants on the Day 1 scan out of all participants with a positive Day 1 scan.
	• Region-level FPR, defined as the proportion of FP regions on the Day 0 scan out of all positive regions on the Day 0 scan.
	• Region-level FPR, defined as the proportion of FP regions on the Day 1 scan out of all positive regions on the Day 1 scan.
To assess the rate of discrepant PET negativity rate of the ⁶⁴ Cu-SAR-bisPSMA PET/CT scans.	Participant-level discrepant PET negativity rate, defined as the proportion of participants with contradicting Day 0 and Day 1 results for whom the Reference Standard was positive.
To assess the TNR of ⁶⁴ Cu-SAR- bisPSMA PET/CT.	• Participant-level TNR, defined as the proportion of TN participants on the Day 0 scan out of all participants with a negative Day 0 scan.
	• Participant-level TNR, defined as the proportion of TN participants on the Day 1 scan out of all participants with a negative Day 1 scan.
	• Region-level TNR, defined as the proportion of TN regions on the Day 0 scan out of all negative regions on the Day 0 scan.

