## 9.14.2 Secondary Efficacy Analyses

The following secondary analyses will be performed in a similar manner as the primary analysis, and will be summarized by central reader with point estimates and exact Clopper-Pearson 95% CI in the FAS and repeated with the PP analysis set:

- Participant-level PPV at Day 0 and Day 1;
  - $\circ$  PPV = TP/(TP + FP) x 100.
- Participant-level Detection Rate (DR) at Day 0 and Day 1;
  - o DR = (number of participants with positive Cu-SAR-bisPSMA PET/CT scan)/(all scanned participants with a Cu-SAR-bisPSMA PET/CT scan) x 100.

September 4, 2024 CONFIDENTIAL Page 30 of 46

- Participant-level False Positive Rate (FPR) on Day 0 and Day 1;
  - $\circ$  FPR = FP/(all scanned participants with a positive Cu-SAR-bisPSMA PET/CT scan and an evaluable reference standard) x 100.
- Region-level FPR at Day 0 and Day 1;
  - $\circ$  FPR = FP regions/(all positive regions on the Cu-SAR-bisPSMA PET/CT scan and an evaluable reference standard) x 100.
- Participant-level discrepant PET negative rate between Day 0 and Day 1 for reference standard positive participants.
- Discrepant PET negative rate;
  - O Discrepant PET negative rate = (number of participants with participant-level discrepancy in Cu-SAR-bisPSMA results between Day 0 and 1) / (all participants with a positive reference standard) x 100.
- Participant-level True Negative Rate (TNR) on Day 0 and Day 1;
  - $\circ$  TNR = TN/(TN+FP) x 100.
- Participant-level Apparent Negative Predictive Value (ANPV; referred to as TNR in the study protocol) on Day 0 and Day 1;
  - o TN/(number of participants with a negative Cu-SAR-bisPSMA result)
- Region-level TNR at Day 0 and Day 1.
  - $\circ$  TNR = TN/(TN+FP) x 100.
- Region-level Apparent Negative Predictive Value (ANPV; referred to as TNR in protocol) at Day 0 and Day 1;
  - o TN/(number of regions with a negative Cu-SAR-bisPSMA result).

Note: Discrepant Day 0 and Day 1  $^{64}$ Cu-SAR-bisPSMA PET/CT results (results differ within subregion from Day 0 and Day 1 within the same central reader) will also be listed.

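### The SAP formula for the discrepant PET negative rate counts reference-negative participants in the numerator but not in the denominator, so it is not a proportion and its exact interval is not valid when such participants exist

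*SAP*

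**What the plan says.** Protocol Table 2 (section 2.7.2) gives no formula. It defines the rate as "the proportion of participants with contradicting Day 0 and Day 1 results for whom the Reference Standard was positive". SAP 3.1.2 repeats that wording.

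SAP 9.14.2 has two adjacent bullets. The first names the endpoint: "Participant-level discrepant PET negative rate between Day 0 and Day 1 for reference standard positive participants". It has no formula under it. The second carries the formula. Its numerator is the "number of participants with participant-level discrepancy in" PET results between Day 0 and Day 1, and its denominator is "all participants with a positive reference standard".

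The secondary rates are to be "summarized by central reader with point estimates and exact Clopper-Pearson 95% CI" in the FAS, and repeated in the Per Protocol set. A note under the list adds a listing of discrepant results, defined at a finer level: "results differ within subregion from Day 0 and Day 1 within the same central reader".

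SAP Table 3 (deviations from protocol analyses) has one entry, on lesion-to-background ratio. The same list in 9.14.2 does flag that the Protocol's TNR is now called ANPV. It flags nothing for the discrepancy rate.

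**The concern.** A rate with an exact binomial interval needs a numerator drawn from its denominator. Here the reference-standard restriction applies to the denominator only. Under SAP 7.8, a reference-negative participant with a positive scan on one day and a negative scan on the other is a false positive on one day and a true negative on the other. He is discrepant, so he is counted on top. He is not reference-positive, so he is not counted below. A rate named for PET negativity thus rises with false positives.

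The SAP also gives one endpoint three descriptions: the wording in 3.1.2, the lead bullet in 9.14.2, and the formula. A programmer who follows the formula and one who follows the bullet above it can produce different tables from the same data.

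Finally, every version pools Day 0 negative/Day 1 positive with Day 0 positive/Day 1 negative. Protocol 2.5.1 justifies the Day 1 scan by a directional hypothesis, that delayed imaging may show smaller lesions. The pooled figure cannot speak to that by itself.

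**Working it through.** The documents give no assumed value, sample size or power for this endpoint, so there is no stated figure to reproduce. The check applies each description to the same hypothetical counts for one reader. **All counts below are assumptions.** The scale is guided by SAP 4.2: 40 evaluable participants and an assumed CDR of 42%, so about 0.42 × 40 = 16.8, or 17, true positives.

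**Notation**
- R = reference-positive participants
- b = reference-positive, Day 0 negative/Day 1 positive
- c = reference-positive, Day 0 positive/Day 1 negative
- e = reference-negative and discrepant

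**Formulas**
- SAP 9.14.2 formula: (b + c + e)/R
- SAP 9.14.2 lead bullet: (b + c)/R
- Literal reading of Protocol Table 2 and SAP 3.1.2: (b + c)/(b + c + e)

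The first two differ by e/R, which is the contribution of reference-negative participants.

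**Illustration 1: R = 25, b + c = 5, e = 3, so 8 discrepant**
- SAP formula: 8/25 = 32%
- Lead bullet: 5/25 = 20%
- Literal Protocol reading: 5/8 = 62.5%
- Excess of formula over lead bullet: 3/25 = 12 points

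If e = 0 with b + c still 5, the formula and the lead bullet both give 5/25 = 20%, and the literal reading gives 5/5 = 100%.

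**Illustration 2: 40 participants, R = 20, b = 6, c = 1, e = 3**

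| Version | Rate | Clopper-Pearson 95% |
|---|---|---|
| SAP formula | 10/20 = 50.0% | 27.2–72.8 (computable, but not valid because 3 of the 10 are outside the 20) |
| Lead bullet | 7/20 = 35.0% | 15.4–59.2 |
| Literal Protocol reading | 7/10 = 70.0% | 34.8–93.3 |
| Day 0 negative/Day 1 positive | 6/20 = 30.0% | 11.9–54.3 |
| Day 0 positive/Day 1 negative | 1/20 = 5.0% | 0.1–24.9 |

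Exchanging b and c (1 and 6) leaves the first three rows unchanged and swaps the last two.

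**Range.** With R of 17, 20, 24 or 28, b + c from 2 to 8, and e from 0 to 6:
- SAP formula: 7% to 82%
- Lead bullet: 7% to 47%
- Literal reading: 25% to 100%
- Excess of formula over lead bullet: 0 to 35 points

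**Boundary case.** With R = 8, b + c = 5 and e = 5, the formula gives 10/8 = 125% and the exact interval cannot be computed. This is an extreme set of counts. It shows that nothing in the formula bounds the result at 100%.

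**The case against.** The best defence is that the intent is clear. The bullet above the formula restricts the endpoint to reference-positive participants, and the denominator does the same, so a sensible programmer would restrict the numerator too. The Protocol phrase is loose enough to carry that meaning. If no discrepant participant is reference-negative, the formula and the bullet give the same number. This stands in part. The Protocol wording is ambiguous, so the 62.5% and 70% figures belong to one reading of it, and it cannot be said that the Protocol flatly contradicts the lead bullet. But the only formula given omits the restriction, and whether e is zero will not be known until the data are in.

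A reader might go further in three ways that the documents do not support.

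- **That participants with one scan dilute the denominator.** SAP 9.14.1 states, for the primary endpoints, that FAS members lacking the results needed to build an outcome do not contribute, and 9.14.2 says the secondary analyses are done similarly. The Per Protocol repeat requires evaluable assessments on both days. The restriction is implied; it only needs stating. Neither provision repairs the numerator.
- **That this is the only analysis bearing on what one scan shows and the other does not.** Day 0 and Day 1 CDR are co-primary, composite CDR and DR are planned (SAP 9.14.3.1), lesion counts on the two days are compared by signed rank test (9.14.3.4), PET-negative/reference-positive cases are summarised as Test Negative (7.8), and discrepant results are listed. Direction can be worked out from these.
- **That the rate, once split, would show which scan missed disease.** Protocol 7.5.2 and SAP 7.8 decline to assign false negatives, because disease may have developed after the scan. A reference-positive man whose PET lesion does not match the reference location, and who has no confirmed PSA response, is classed as a false positive. The split rate would still count him as PET-positive on that day.

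**Conclusion.** The formula in SAP 9.14.2 is wrong as written. Its numerator is not a subset of its denominator, reference-negative discrepant participants inflate it by e/R, and the planned exact interval is not valid whenever e is above zero. It also departs from the bullet above it and from the literal wording elsewhere, without an entry in SAP Table 3.

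In the first illustration the inflation is 12 points (32% against 20%). Across the assumed grid it runs from 0 to 35 points. These sizes rest entirely on assumed counts and on both scans being evaluable; the documents supply none of them.

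The reach is limited. This is one descriptive secondary endpoint. SAP 4.1 plans no formal hypothesis test, and no sample size depends on it. It should be corrected because a stated rule can yield a wrong number. It does not threaten the primary results or leave the study unable to compare the two scan days.

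**What to change.** In SAP 9.14.2, merge the two bullets into one definition, applied per central reader:
- **Numerator:** reference-positive participants whose Day 0 and Day 1 participant-level PET results differ.
- **Denominator:** reference-positive participants with both scans evaluable for that reader.

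In the same table, report the Day 0 negative/Day 1 positive and Day 0 positive/Day 1 negative components, each with an exact interval, above their total. Describe them as PET-negative with a positive Reference Standard, not as missed disease or false negatives.

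Align SAP 3.1.2 with this definition, and record the clarification of the Protocol wording in SAP Table 3.

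The cost is a wording change (an SAP amendment if the plan is already signed), two extra table rows, and a denominator that may be slightly smaller. No new data are needed.

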7.5.2 Assessment of Reference Standard against the ⁶⁴Cu-SAR-bisPSMA PET/CT Results

For the assessment of the Reference Standard against the ⁶⁴Cu-SAR-bisPSMA PET/CT, region-level matching will be used for histopathology, subregion-level matching for imaging and participant-level matching for PSA response to radiation or other salvage focal therapy (refer to Section 7.5.1). Matching of the Reference Standard against the ⁶⁴Cu-SAR-bisPSMA PET/CT results will be completed via statistical programming.

Assessment of **region-level** Reference Standard against the ⁶⁴Cu-SAR-bisPSMA PET/CT results:

- Histopathology: A region that is ⁶⁴Cu-SAR-bisPSMA PET-positive (i.e., includes at least one unequivocal PET-positive lesion) and Reference Standard positive, will be assigned as true positive (TP) for the region-level status.
- Imaging: A subregion that is ⁶⁴Cu-SAR-bisPSMA PET-positive (i.e., includes at least one unequivocal PET-positive lesion) and Reference Standard positive (i.e., includes at least one unequivocal lesion detected on conventional imaging in that subregion), will be assigned as TP. A region that includes at least one TP subregion will be assigned as TP for the region-level status.
- A region that is ⁶⁴Cu-SAR-bisPSMA PET-positive (i.e., includes at least one unequivocal PET-positive lesion) and is Reference Standard negative based on at least 1 evaluable timepoint, will be assigned as false positive (FP) for the region-level status.
- A region that is ⁶⁴Cu-SAR-bisPSMA PET-negative (i.e., no unequivocal PET-positive lesion or only equivocal lesion(s) detected within the subregions) and Reference Standard negative, will be assigned as true negative (TN) for the region-level status.
- A region that has either non-evaluable ⁶⁴Cu-SAR-bisPSMA result for a specific timepoint or has a non-evaluable or inconclusive Reference Standard will not be assigned for that timepoint.

Assessment of **participant-level** Reference Standard against the ⁶⁴Cu-SAR-bisPSMA PET/CT results:

- A participant with at least one TP region AND/OR at least one unequivocal ⁶⁴Cu-SARbisPSMA PET-positive lesion and confirmed PSA response to radiation or other salvage focal therapy, will be assigned as TP for the participant-level status.
- A participant with at least one unequivocal ⁶⁴Cu-SAR-bisPSMA PET-positive lesion who does not meet the above criteria to be deemed TP, will be assigned as FP for the participant-level status.

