#### • False Positive:

 A region that is Cu-SAR-bisPSMA PET-positive (i.e., includes at least one unequivocal PET-positive lesion) and Reference Standard negative based on at least 1 evaluable timepoint.

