## • Non-evaluable:

o A region that has either non-evaluable (NE) Cu-SAR-bisPSMA PET/CT results for a specific timepoint (Day 0 or Day 1) or has a non-evaluable or inconclusive Reference Standard will not be assigned for that timepoint.

Assessments of **Participant-Level** Reference Standard against the Cu-SAR-bisPSMA PET/CT results:

• True Positive:

September 4, 2024 CONFIDENTIAL Page 22 of 46

- A participant with at least one TP region and/or at least one unequivocal Cu-SAR-bisPSMA positive lesion in any region and a confirmed PSA response to radiation or other salvage focal therapy.
  - Confirmed PSA response following radiation or other salvage focal therapy (as long as no concomitant ADT is given) = total PSA decline ≥50% from baseline, confirmed by a 2nd value within 4 weeks per Prostate Cancer Working Group 3 criteria.

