#### • True Negative:

 A participant with a negative Cu-SAR-bisPSMA PET/CT (i.e., no unequivocal PET-positive lesion or only equivocal lesion(s) detected) and negative Reference Standard.

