## • False Positive:

• A participant who does not meet the TP criteria and has at least one unequivocal Cu-SAR-bisPSMA PET-positive lesion and has an evaluable Reference Standard.

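### The participant-level TN/(TN+FP) rate added in SAP 9.14.2 can count reference-positive men in its denominator, because participant-level FP does not require a negative Reference Standard

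*SAP*

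**What the plan says.** **The rate.** SAP 9.14.2 includes "Participant-level True Negative Rate (TNR) on Day 0 and Day 1" among the secondary analyses, with the formula "TNR = TN/(TN+FP) x 100". The same formula is used at region level. The next participant-level entry is the Apparent Negative Predictive Value (ANPV), TN over participants with a negative scan, which the SAP identifies as what the protocol calls TNR. Protocol 2.7.2 and SAP 3.1.2 do define TNR that way, with the negative scans as denominator. SAP 9.14.2 therefore reports two quantities, and the one labelled TNR is not the one that SAP 3.1.2 defines.

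**The classes (SAP 7.8).**
- Participant-level TN: a PET-negative scan, with "only equivocal lesion(s) detected) and negative Reference Standard".
- Participant-level FP: "A participant who does not meet the TP criteria and has at least one unequivocal" "PET-positive lesion and has an evaluable Reference Standard". Protocol 7.5.2 has the same residual rule: a PET-positive man "who does not meet the above criteria to be deemed TP, will be assigned as FP for the participant-level status".
- Participant-level TP: "A participant with at least one TP region and/or at least one unequivocal" PET-positive lesion together with a confirmed PSA response to radiation or other salvage focal therapy. A TP region needs a match by region for histopathology or by subregion for imaging.
- Region-level FP: PET-positive and "Reference Standard negative based on at least 1 evaluable timepoint".
- A PET-negative participant with a positive Reference Standard is labelled Test Negative, for summary purposes only. He is neither TN nor FP.

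**The concern.** TN/(TN+FP) has the form of a true negative rate: the share of reference-negative units that the scan calls negative. It is that rate only if everyone counted in TN and FP is reference-negative.

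At region level this holds, because both classes require a negative Reference Standard. At participant level it need not hold. FP is whatever remains of the PET-positive men once the TP men are removed. That suits PPV and FPR, where a positive scan not confirmed at its location should count against the scan. It does not suit a rate meant to describe men without reference disease.

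Reference-positive men are also treated unevenly. If PET-negative, they are Test Negative and stay out of TN+FP. If PET-positive at a site that does not match, they go in. The rate would then move with localisation in men who have disease, and the participant-level and region-level rows would measure different things under one name and one formula.

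**Working it through.** **1. The plan's own figures.** The documents state no expected TNR, so there is no figure to reproduce for this rate. The neighbouring planning figures do reproduce:
- CDR: with n = 40, the smallest count whose exact 95% lower bound exceeds 20% is 14 (lower bound 20.6%). Power at 42% is 85.5%, consistent with the stated more than 85%.
- Region-level PPV: 40 × 0.65 × 1.3 = 33.8, or about 34 regions. The smallest count with a lower bound above 40% is 20, and power at 65% is 82.6%, consistent with more than 80%.

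**2. How a reference-positive man becomes FP.** Take a man with an unequivocal PET lesion in the left pelvic nodes. The reference imaging shows an unequivocal lesion only in the right pelvic nodes, which is a separate subregion in SAP Table 2. He has no histopathology and no confirmed PSA response.
- TP? No: there is no matching subregion and no PSA response.
- FP? Yes: he is PET-positive, not TP, and his Reference Standard is evaluable.
- TN? Never: he is PET-positive, and his Reference Standard is not negative.

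A man who is reference-positive through PSA response alone cannot cause this, because PET-positive plus confirmed PSA response is TP.

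**3. Direction.** Let m be the number of FP men with a positive Reference Standard.
- Rate as written: TN/(TN+FP).
- Rate among reference-negative men: TN/(TN+FP−m).

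The first is strictly lower whenever m ≥ 1 and TN > 0. The two are equal when m = 0.

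**4. Size.** From SAP 4.2:
- PET-positive: 40 × 0.65 = 26.
- TP: 40 × 0.42 = 16.8, taken as 17.
- FP: 26 − 16.8 = 9.2, taken as 9.
- PET-negative: 40 − 26 = 14.

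The split of the 14 PET-negative men into 8 TN and 6 Test Negative is an assumption, and so is m. Neither has a source in the documents.

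| m | As written | Among reference-negative men | Gap (points) |
|---|---|---|---|
| 0 | 8/17 = 47.1% | 8/17 = 47.1% | 0 |
| 1 | 47.1% | 8/16 = 50.0% | 2.9 |
| 2 | 47.1% | 8/15 = 53.3% | 6.3 |
| 3 | 47.1% | 8/14 = 57.1% | 10.1 |
| 4 | 47.1% | 8/13 = 61.5% | 14.5 |

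Varying the assumed TN count, with FP = 9:

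| TN | As written (also m = 0) | m = 1 | m = 3 | m = 5 |
|---|---|---|---|---|
| 14 | 60.9% | 63.6% | 70.0% | 77.8% |
| 10 | 52.6% | 55.6% | 62.5% | 71.4% |
| 7 | 43.8% | 46.7% | 53.8% | 63.6% |
| 4 | 30.8% | 33.3% | 40.0% | 50.0% |

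The gap is about 3 points for one mismatched man, 9 to 10 for three and 17 to 20 for five, and it depends little on TN.

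**5. What does not move.** CDR counts only TP in its numerator and does not use FP. Region-level PPV and region-level TNR use region-level FP, which requires a negative reference. ANPV has negative scans as its denominator, so FP does not enter it.

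**The case against.** **A reader might infer that the protocol's secondary TNR endpoint is biased.** The documents do not support that. The protocol defines TNR over negative scans, and SAP 9.14.2 still reports that quantity as ANPV. Only the added rate is exposed. This part of the objection stands in full.

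**A reader might also infer that a downward bias is established.** It is not. The shift is zero unless at least one PET-positive man is reference-positive solely at non-matching sites. The documents give no frequency for this. They do give reasons why it could happen: SAP Table 2 has 23 subregions with many left/right splits, the reference panel does not see the study scans, and Protocol 7.5.2 chose the 90- and 180-day follow-up so that disease could develop further. These make mismatch plausible but do not measure it.

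**The target can be disputed.** Protocol 7.5.2 warns that a positive follow-up scan may reflect disease that arose after the study scan. A man with new disease at another site on Day 90 or 180 may not have had it at scan time, and removing him from the denominator treats follow-up status as scan-time status. The caution is fair, but it does not rescue the formula. The same caution leads the plan to keep PET-negative, reference-positive men out of TN+FP, so counting only their PET-positive counterparts is inconsistent.

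**The programming may already handle it.** SAP 7.8 refers the full algorithm to a supplemental spreadsheet, which is not among the documents. A restriction there cannot be ruled out, but the SAP text should still state it.

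**The consequences are limited.** No formal hypothesis testing is planned and no success rule uses this rate. On the assumed counts, the exact 95% interval for 8/17 runs from 23.0% to 72.2% and covers every alternative value in the first table. SAP 9.12 and 9.13 already provide listings from which mismatched men could be found. All of this limits the importance of the point, but a wide interval does not make a misdefined denominator right.

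**Conclusion.** The point holds for one added secondary rate. As the SAP is written, participant-level TN/(TN+FP) is not guaranteed to be a rate among reference-negative men. Any departure is downward, and its size is set by the number of location-mismatched, reference-positive FP men. With the assumed 9 FP and 8 TN, 0 to 4 such men give a gap of 0 to 14.5 points. FP of about 9 follows from the planning values; the TN count and the number of mismatched men are assumptions. No primary endpoint and no protocol-defined endpoint is affected.

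A related inconsistency belongs with it. SAP 3.1.2 and 9.14.2 attach the name TNR to different quantities, and SAP Table 3 does not list the added rate as a departure from the protocol analyses.

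**What to change.** 1. In SAP 9.14.2, define the added participant-level TNR as TN divided by all participants with an evaluable PET at that timepoint and a negative participant-level Reference Standard.
2. Keep the existing participant-level FP definition for PPV and FPR.
3. Report, by reader and timepoint, the number of FP men whose Reference Standard is positive at a non-matching site.
4. Align SAP 3.1.2 with 9.14.2, so that TN over negative scans and the added rate have distinct names throughout, and list the added rate in SAP Table 3. Confirm that the supplemental analysis document follows the same rule.

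**Cost.** One formula line, one programming condition, one count and a few lines of text. The denominator is slightly smaller if mismatches occur, so the interval widens a little. On the assumed counts, it goes from 23.0%–72.2% for 8/17 to 28.9%–82.3% for 8/14 (width 49.2 to 53.4 points). No new data are needed.
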